9.5.3 Liver toxicity

HCC patients are at risk for a range of complications that can cause hepatic laboratory abnormalities with or without clinical decompensation. Moreover, temporary hepatic decompensation may occur especially in cirrhotic patients when exposed to a TKI.

It may be difficult to distinguish these lab abnormalities related to cabozantinib from immune-mediated hepatitis of pembrolizumab. Grade 3 immune-related hepatitis was observed in 3% of patients who received pembrolizumab in the KEYNOTE-224 trial,³⁵ while 7% of patients treated with pembrolizumab in

the KEYNOTE-240 trial experienced an immune-mediated hepatic event, although no HBV/HCV flares occurred.³⁶ Previous studies showed that immune-mediated hepatitis typically occurs during the first 6-12 weeks after initiating an immune checkpoint inhibitor.⁵⁹ Those with a history of chronic HCV or HBV infection also have the potential to experience virologic flares.

Hepatic events of clinical interest (HECI) are defined as:

- ALT:
 - a: Among subjects with baseline ALT <2×ULN: ALT ≥5×ULN
 - b: Among subjects with baseline ALT ≥2×ULN: ALT >3× the baseline level
 - c: ALT >500 U/L regardless of baseline level
- Total bilirubin:
 - a: Total bilirubin >3.0 mg/dL
- Regardless of laboratory values, hepatic decompensation diagnosed clinically, including:
 - New onset clinically detectable ascites requiring intervention for >3 days
 - Hepatic encephalopathy

General management for liver toxicity:

- In the setting of liver toxicity indicated by abnormal liver function tests (e.g. ALT, AST, ALP, total bilirubin, INR), monitor liver function **at least weekly** until recovery to baseline or stabilization.
- If there is grade 3 hepatic toxicity, it is recommended that both cabozantinib and pembrolizumab be interrupted and the patient be further evaluated. Consider causes of hepatitis and obtain appropriate workup, including disease progression, viral causes (HBV, HCV, EBV, CMV), drug- or alcohol-induced hepatitis, herbals, infection, biliary obstruction, etc.
- When an HECI occurs:
 - Hold study intervention and notify the Principal Investigator within 24 hours. All cases of retreatment after interruption of study intervention for HECI must be reported to the Principal Investigator and recorded in the database.
 - All participants should be considered for evaluation according to the directions below within 72 hours of onset:
 - Consider obtaining a consultation with a hepatologist.
 - Obtain a work-up for hepatitis if there is no underlying hepatitis, including hepatitis A, B, C, D, E, Epstein-Barr virus, and cytomegalovirus.
 - Assess for ingestion of drugs/supplements with hepatotoxic potential.
 - Assess for alcohol ingestion.
 - Assess for potential bacterial infection, biliary obstruction, or occultgastrointestinal bleeding.
 - Repeat ALT, AST, total bilirubin, direct bilirubin, alkaline phosphatase, γ-glutamyl transpeptidase, INR, and complete blood count with differential.
 - Measure HCV RNA viral load (applies only for participants who have current active HCV infection or had infection in the past).
 - HBV DNA, HBsAg, HBeAg, HBcAb (total and IgM), HBeAb, and HBsAb regardless of prior HBV status (Note: participants should be questioned about compliance with the use of antiviral agents).
 - Other laboratories or imaging studies as clinically indicated.
 - Consider liver biopsy if indicated. In the setting of HBV flare or change in HBV immunologic status:
 - Start antiviral therapy if appropriate

- Measure HBsAg and HBV DNA on **weekly** basis (if detected at the time of onset of HECI).
- Evaluate the following every 2-3 weeks if not detected at the time of onset of HECI
 - Anti-HBe, HBe antigen, anti-HBs, and HBV DNA levels (if not detected at the onset of HECI)
- In the setting of HCV exacerbation in patients with positive HCV RNA, relapse of HCV in patients with previous antiviral treatment, or new HCV infection:
 - Recheck HCV genotype at the time of relapse of HCV RNA to rule out new infection.
 - Measure HCV RNA levels **every 2 weeks**.
- Please discuss risk benefit with Principal Investigator prior to starting HCV antiviral therapy.- If there are other causes of liver dysfunction, treat accordingly (e.g. biliary obstruction).
- The following table provides guidance on the dosing of cabozantinib and pembrolizumab in the setting of non-immune liver toxicity.
- If there is suspicion for possible pembrolizumab-mediated hepatitis, also follow the management outlined in Table 9.5.5.1:
- Cabozantinib may be held up to 28 days, and pembrolizumab may be held up to 12 weeks.
- Elevations $>3 \times$ ULN of ALT or AST concurrent with $>2 \times$ ULN total bilirubin without other explanation can indicate drug-induced liver injury (DILI) due to cabozantinib. Cabozantinib should be permanently discontinued in cases determined to be DILI according to Hy's Law review.
- Study treatment should be discontinued indefinitely if grade 3 hepatic dysfunction is not reversed despite dose interruption and treatment of potential causes including immune-mediated hepatitis.

Table 9.5.3.1. Guidance for liver toxicity due to cabozantinib (non-immune)

Grade per CTCAE v5	Cabozantinib modification ¹	Pembrolizumab modification ¹
ALT/AST $> 5 \times$ ULN if ALT/AST $\leq 2 \times$ ULN at baseline OR ALT/AST 3-fold increase from D1 level BUT NOT EXCEEDING $8 \times$ ULN if ALT/AST $> 2 \times$ ULN at baseline	
 • Hold drug until recovery to \leq grade 2 ALT/AST elevation, then restart at reduced dose (consider resume at the same dose if other cause of liver toxicity found). • 1st recurrence: discontinued drug. 	
 • Hold drug until recovery to grade 1 (or pretreatment baseline), then restart drug.
ALT or AST $> 5 \times$ ULN accompanied by total bilirubin $\geq 2 \times$ ULN	
 • Hold drug until recovery to \leq grade 1 ALT/AST and bilirubin elevation or pre-treatment baseline, then restart at reduced dose (consider resume at the same dose if other cause of liver toxicity found). • 1st recurrence: discontinue. • Note: A patient with Gilbert's syndrome should be managed according to observed elevation of ALT and/or AST if the observed bilirubin increase is below actual increased baseline bilirubin value. 	
 • Hold drug until recovery to grade 1 (or pretreatment baseline), then restart drug.

Total bilirubin > 3.0 mg/dL irrespective of ALT/AST values	
 Hold drug until recovery to ≤ grade 1 ALT/AST and bilirubin elevation, then restart at reduced dose (consider resume at the same dose if other cause of liver toxicity found). 1st recurrence: discontinue. 	
 Hold drug until recovery to grade 1 (or pretreatment baseline), then restart drug.
	
 Note: For a patient with Gilbert's syndrome, a continuation of cabozantinib might be considered at the discretion of the investigator if the observed bilirubin increase is below actual increased baseline bilirubin value. 	
AST and/or ALT > 20 x ULN	
 Discontinue drug. 	
 Hold drug until recovery to grade 1 (or pretreatment baseline), then restart drug.
Hepatic encephalopathy not reversible and manageable by therapy ²	
 Discontinue drug.² 	
 Discontinue drug.²
Child-Pugh score > 8 points ²	
 Discontinue drug.² 	
 Hold drug until Child-Pugh score < 8, then resume at drug.²
GI bleeding suggestive or portal hypertension (e.g. esophageal or gastric varices)	
 Discontinue drug. 	
 Hold drug until bleeding has resolved and intervention completed if indicated (e.g. variceal banding) and patient is stable, then restart at the same dose as long as Child-Pugh score < 8 and ALT/AST/bilirubin elevations are < grade 3.

¹Once dose reduced, cabozantinib dose cannot be increased. Cabozantinib may be held up to 28 days, and pembrolizumab may be held up to 12 weeks.

²Some TKIs may cause hepatic encephalopathy, which is reversible and manageable. Patients with transient deterioration to Child Pugh score > 8 due to an ongoing reversible process such as treatable infection or dehydration can be reassessed for up to 2 weeks; if liver function improves to Child Pugh 5-7, consider reintroduction of pembrolizumab monotherapy and subsequent reintroduction of cabozantinib 1-2 weeks later if Child Pugh is 5-6 after discussion with study PI.

9.5.4 Skin toxicity other than PPES

Dose modification of cabozantinib for hand-foot reaction (or PPES) is covered in Section 9.3.7. Other skin rashes or abnormalities may occur due to cabozantinib.

General management of skin toxicities:

- Optimize supportive measures, including topical emollients, oral antihistamines, and medium- to high potency topical corticosteroids.
- For grade 2 and higher skin toxicity, monitor weekly for improvement.

- For grade 3 skin toxicity, consider referral to Dermatology.
- If a grade 3 rash does not improve within 7 days after stopping cabozantinib and pembrolizumab and providing optimal supportive measures, suspect immune-mediated skin toxicity.
- See Table 9.5.4.1 for dosing of cabozantinib and pembrolizumab for non-immune mediated skin toxicity. For immune-mediated skin toxicity, see Table 9.5.5.1.

Table 9.5.4.1. Guidance for non-immune skin and subcutaneous toxicity other than PPES (e.g. rash, erythematous, follicular, macular, dermatitis, pruritis).		
Grade per CTCAE v5	Cabozantinib modification	Pembrolizumab modification
Grade 1 or 2	
 • Continue at the same dose level. 	
 • Continue at the same dose level.
Grade 3	
 • Hold drug until recovery to grade 2 or less, then restart at same dose or at reduced dose (at the discretion of the investigator). • 1st and 2nd recurrence: hold until recovery to grade 2 or less, then restart at reduced dose level (if not already reduced) or discontinue drug (if previously reduced dose). 	
 • Hold drug until recovery to grade 1 (or pretreatment baseline), then restart drug.
Grade 4 or Steven Johnson Syndrome of any grade	
 • Hold drug until recovery to grade 2 or less, then restart at reduced dose. • 1st recurrence: discontinue drug. 	
 • Hold drug until recovery to grade 1 (or pretreatment baseline), then restart drug.

9.5.5 Immune-related toxicities

Immune-related AEs (irAEs) may occur after the first dose or several months later. Workup should be performed to rule out other causes. Most irAEs are reversible when the immune checkpoint inhibitor is stopped and steroids and supportive care are initiated. Depending on severity of irAEs, pembrolizumab may be resumed after recovery (after completion of steroid taper) or permanently discontinued.

The ASCO Clinical Practice Guidelines on the Management of Immune-Related Adverse Events in Patients Treated with Immune Checkpoint Inhibitor Therapy⁵⁸ provides a comprehensive overview of potential irAEs and management. Whenever possible, it is recommended that these guidelines be followed.

General management for irAEs:

- Consider other causes and ensure adequate workup to rule out other etiology if applicable (e.g. infectious, drug-induced).
- Please see Table 9.5.5.1 for guidance on pembrolizumab dosing for specific irAEs. Whenever pembrolizumab is held for an irAE, cabozantinib should also be held. The latter can be resumed when the irAE improves to grade 1 (even if pembrolizumab has not been restarted yet, e.g. during steroid taper).

Table 9.5.5.1. Dose modification and toxicity management guidelines for other immune-related AEs..

General instructions:				
Immune-related AEs	Toxicity grade or conditions (CTCAEv5.0)	Action taken to pembrolizumab	irAE management with corticosteroid and/or other therapies	Monitor and follow-up
Pneumonitis	Grade 2	Withhold	
 Administer corticosteroids (initial dose of 1-2 mg/kg prednisone or equivalent) followed by taper 	
 Monitor participants for signs and symptoms of pneumonitis Evaluate participants with suspected pneumonitis with radiographic imaging and initiate corticosteroid treatment Add prophylactic antibiotics for opportunistic infections
	Grade 3 or 4, or recurrent Grade 2	Permanently discontinue		
Type 1 diabetes mellitus (T1DM) or Hyperglycemia	Newly onset T1DM or Grade 3 or 4 hyperglycemia associated with evidence of β -cell failure	Withhold	
 Initiate insulin replacement therapy for participants with T1DM Administer anti-hyperglycemic in participants with hyperglycemia 	
 Monitor participants for hyperglycemia or other signs and symptoms of diabetes.

Hypophysitis	Grade 2	Withhold	
 Administer corticosteroids and initiate hormonal replacements as clinically indicated. 	
 Monitor for signs and symptoms of hypophysitis (including hypopituitarism and adrenal insufficiency)
	Grade 3 or 4	Withhold or permanently discontinue ¹		
Hyperthyroidism	Grade 2	Continue	
 Treat with non-selective beta-blockers (eg, propranolol) or thionamides as appropriate 	
 Monitor for signs and symptoms of thyroid disorders.
	Grade 3 or 4	Withhold or permanently discontinue ¹		
Hypothyroidism	Grade 2-4	Continue	
 Initiate thyroid replacement hormones (eg, levothyroxine or liothyroinine) per standard of care 	
 Monitor for signs and symptoms of thyroid disorders.
Nephritis and Renal dysfunction	Grade 2	Withhold	
 Administer corticosteroids (prednisone 1-2 mg/kg or equivalent) followed by taper. 	
 Monitor changes of renal function
	Grade 3 or 4	Permanently discontinue		
Myocarditis	Grade 1 or 2	Withhold	
 Based on severity of AE administer corticosteroids Cabozantinib must be held until resolved to grade 0. 	
 Ensure adequate evaluation to confirm etiology and/or exclude other causes
	Grade 3 or 4	Permanently discontinue		
All other immune-related AEs	Intolerable/persistent Grade 2	Withhold	
 Based on type and severity of AE administer corticosteroids 	
 Ensure adequate evaluation to confirm etiology and/or exclude other causes
	Grade 3	Withhold or discontinue based on the type of event. Events that require discontinuation include and not limited to: Gullain-Barre Syndrome, encephalitis		
	Grade 4 or recurrent Grade 3	Permanently discontinue		

1. Withhold or permanently discontinue pembrolizumab is at the discretion of the investigator or treating physician.

NOTE:

For participants with Grade 3 or 4 immune-related endocrinopathy where withhold of pembrolizumab is required, pembrolizumab may be resumed when AE resolves to ≤ Grade 2 and is controlled with hormonal replacement therapy or achieved metabolic control (in case of T1DM).

9.5.6 Pembrolizumab-related infusion reaction

Pembrolizumab may cause severe or life-threatening infusion-reactions including severe hypersensitivity or anaphylaxis. Signs and symptoms usually develop during or shortly after drug infusion and generally resolve completely within 24 hours of completion of infusion. Dose modification and toxicity management guidelines on pembrolizumab associated infusion reaction are provided in Table 9.5.6.1. No dose modification is required for cabozantinib.

Table 9.5.6.1. Pembrolizumab infusion reaction dose modification and treatment guidelines

NCI CTCAE grade	Treatment	Premedication at subsequent dosing
Grade 1 Mild reaction; infusion interruption not indicated; intervention not indicated	Increase monitoring of vital signs as medically indicated until the participant is deemed medically stable in the opinion of the investigator.	None
Grade 2 Requires therapy or infusion interruption but responds promptly to symptomatic treatment (e.g. antihistamines, NSAIDs, narcotics, IV fluids); prophylactic medications indicated for ≤24 hrs	
Stop Infusion.
 
Additional appropriate medical therapy may include but is not limited to:
 
 • IV fluids • Antihistamines • NSAIDs • Acetaminophen • Narcotics 
Increase monitoring of vital signs as medically indicated until the participant is deemed medically stable in the opinion of the investigator.
 
If symptoms resolve within 1 hour of stopping drug infusion, the infusion may be restarted at 50% of the original infusion rate (e.g. from 100 mL/hr to 50 mL/hr). Otherwise dosing will be held until symptoms resolve and the participant should be premedicated for the next scheduled dose.
 
Participants who develop grade 2 toxicity despite adequate premedication should be permanently discontinued from further study drug treatment.
	Participant may be premedicated 1.5h (± 30 minutes) prior to infusion of pembrolizumab with: Diphenhydramine 50 mg PO/IV (or equivalent dose of antihistamine). Acetaminophen 500-1000 mg PO (or equivalent dose of analgesic).

Grades 3 or 4 Grade 3: Prolonged (i.e. not rapidly responsive to symptomatic medication and/or brief interruption of infusion); recurrence of symptoms following initial improvement; hospitalization indicated for other clinical sequelae (e.g. renal impairment, pulmonary infiltrates) Grade 4: Life-threatening; pressor or ventilatory support indicated	Stop Infusion. Additional appropriate medical therapy may include but is not limited to: 
 • Epinephrine** • IV fluids • Antihistamines • NSAIDs • Acetaminophen • Narcotics • Oxygen • Pressors • Corticosteroids Increase monitoring of vital signs as medically indicated until the participant is deemed medically stable in the opinion of the investigator. Hospitalization may be indicated. **In cases of anaphylaxis, epinephrine should be used immediately. Participant is permanently discontinued from further study drug treatment.	No subsequent dosing
Appropriate resuscitation equipment should be available at the bedside and a physician readily available during the period of drug administration. For further information, please refer to the CTCAEv5 at http://ctep.cancer.gov .		

9.6 Adverse events not related to study drugs

If an AE is unrelated to either cabozantinib or pembrolizumab (e.g. symptoms due to disease, concomitant medication/procedure, other illness), cabozantinib and pembrolizumab may be continued or held at the discretion of the investigator. In general, treatment may be continued if the AE is not treatment-related and not clinically significant, the patient is relatively asymptomatic and stable with good performance status, and if treatment will not delay recovery or worsen the AE. **If treatment is held for AEs unrelated to treatment, cabozantinib and pembrolizumab should be resumed at the same doses as previously within 4 weeks.**

10.0 STUDY CALENDAR

Table 10.1 summarizes the trial procedures to be conducted at various timepoints. It may be necessary to perform these procedures at unscheduled time points if deemed clinically necessary by the investigator. Furthermore, additional evaluations/testing not outlined in this table may be deemed necessary by the Principal Investigator for reasons related to participant safety.

Table 10.1. Baseline schedule of activities

1 cycle = 21 days	Baseline ¹⁷	Cycle 1			Cycle 2+ Day 1 (± 2 days)	Treatment discontinuation visit ¹⁹ (+ 7 days)	Follow-up ²⁰ (± 7 days)
		Day 1 ¹⁸	Day 8 (± 2 days)	Day 15 (± 2 days)			
TREATMENT							
Cabozantinib ¹		X	X	X	X		
Pembrolizumab ²		X			X		
REQUIRED ASSESSMENTS							
Informed consent/HIPAA	X						
Inclusion/exclusion criteria ³	X						
Medical and smoking history	X						
Disease and treatment history	X						
Vital signs, physical exam, ECOG status, weight ⁴	X	X	X	X	X	X	
Height ⁵	X						
AE and medications assessment ⁶	X	X	X	X	X	X	
Cabozantinib Drug Diary Collection ⁷		X			X	X	
CBC and differential ⁸	X	X		X	X	X	
Serum chemistry ⁸	X	X		X	X	X	
PT/INR, PTT	X	X			X	X	
Lactate dehydrogenase	X						
Hepatitis C antibody (+/- HCV RNA) ⁹	X						
Hepatitis B core antibody ¹⁰	X						
Hepatitis B surface antigen and/or HBV	X				X (q2C starting)		

DNA ¹⁰					at C3)		
TSH with reflex T4 ¹¹	X				X (q2C starting at C3)		
Cortisol ¹¹	X				X (q2C starting at C3)		
Amylase ¹¹	X				X (q2C starting at C3)		
Lipase ¹¹	X				X (q2C starting at C3)		
Urinary protein to creatinine ratio ¹¹	X				X (q2C starting at C3)		
EKG ¹¹	X				X (q2C starting at C3)		
Esophagoduodenoscopy (EGD) ¹²	X						
Pregnancy test (WOCOP only)	X						
Vital status, date of progression if applicable						X	X
DISEASE ASSESSMENT							
Alpha fetoprotein ¹³	X				X (q3C starting at C4)	X	
Radiologic imaging by CT or MRI ¹⁴	X				X (q3C starting at C4)	X	X
CORRELATIVE STUDIES							
Archival tumor tissue for research purposes if available. Otherwise, fresh biopsy is optional. ¹⁵	X						
Blood collection ¹⁶		X	X		X (C2D1 only)		

Footnotes

¹Daily continuously starting at Cycle 1 Day 1. See Section 9.0 for dose modifications.

²Dosed on Day 1 of each 3-week cycle. See Section 9.0 for dose modifications.

³See Section 5.0 for inclusion and exclusion criteria.

⁴Vital signs include: blood pressure, pulse, respiratory rate, oxygen saturation, temperature. Blood pressure and pulse should be taken at rest while sitting. Physical exam should be performed at baseline, on Day 1 of each cycle, and at the treatment discontinuation visit. A focused physical exam may be

RG1007034

performed if clinically indicated at Cycle 1 Day 8 and 15.

⁵Height only needs to be obtained at baseline.

⁶AE assessment using CTCAE v5. All TRAEs will be followed until resolution, return to baseline, or deemed clinically insignificant by the treating investigator, including those that occur during the 30-day period after treatment discontinuation. In addition, any SAE related to treatment occurring more than 30 days after treatment discontinuation will be followed until either resolution, return to baseline, or determination by the investigator that the event has become stable or irreversible.

⁷A new diary will be distributed on Day 1 of each cycle and collected on Day 1 of the next cycle. See Appendix 2 for a template of the Cabozantinib Drug Diary.

⁸CBC and differential includes: hemoglobin, hematocrit, leukocyte count, neutrophils (segmented and bands), lymphocytes, monocytes, eosinophils, basophils, and platelets. Serum chemistry includes: sodium, bicarbonate, potassium, calcium, magnesium, phosphate, glucose, albumin, total protein, blood urea nitrogen, creatinine, alanine aminotransferase, aspartate aminotransferase, alkaline phosphatase, and total bilirubin. In addition to the scheduled labs as indicated in the table, more frequent lab monitoring may be initiated by the investigator in the event of AEs.

⁹HCV RNA is obtained if hepatitis C virus antibody (HCV Ab) is positive. There is no need to repeat serology or RNA during the study.

¹⁰If hepatitis B virus core antibody (HBcAb) and surface antigen (HBsAg) at baseline are negative, no further testing is needed. If HBcAb+ and/or HBsAg+, HBV DNA should be obtained at baseline. If a patient is HBcAb+ and HBsAg- at baseline, HBsAg should be obtained every 2 cycles on study starting at cycle 3 and HBV DNA is obtained if HBsAg becomes positive. If a patient is HBcAb+ and HBsAg+, HBV DNA should be obtained every 2 cycles on study starting at cycle 3.

¹¹These tests should be obtained at baseline (within 14 days prior to registration) and repeated every 2 cycles on study starting at cycle 3.

¹²EGD must be done within 6 months prior to study initiation to assess for and treat esophageal and gastric varices.

¹³Alpha fetoprotein (AFP) should be measured at baseline (within 14 days prior to registration). If abnormal at baseline, it should be measured on Day 1 of every 3 cycles starting at cycle 4, and at the treatment discontinuation visit.

¹⁴Disease assessment using multiphasic (four-phase) contrast CT or MRI of abdomen/pelvis, as well as CT chest with or without contrast should be done at baseline (within 28 days prior to registration), and every 9 weeks on treatment (every 3 cycles). If there is disease progression and the patient continues on treatment beyond progression, repeat imaging must be performed 4 weeks later to confirm progression. As clinically indicated, bone scan and contrast imaging of neck may be obtained to monitor disease (see Section 13.3). For the treatment discontinuation visit, the most recent scans are used. For patients who come off study for toxicity, subsequent restaging scans will be requested and assessed at least every 4 months for up to 2 years from study start date to document the date of progression.

¹⁵Archival tumor tissue is acceptable (paraffin-embedded tumor core biopsy or surgical specimen). If archival tissue is not available, baseline core needle biopsy may be performed (if safe and feasible).

¹⁶Pre-treatment Blood will be collected and stored for correlative studies. Research blood will be collected on Cycle 1 Day 1 and Day 8, as well as Cycle 2 Day 1.

¹⁷Informed consent/HIPAA, medical/smoking history, AE/medication assessment, physical exam/ECOG, and assessment of inclusion/exclusion criteria are completed within 28 days prior to registration. Baseline lab investigations are completed within 14 days prior to registration, including pregnancy test for women of child-bearing potential (WOCP) and AFP. Baseline imaging for disease assessment may be obtained within 28 days prior to registration.

¹⁸Cycle 1 day 1 testing need not be repeated if completed within 7 days prior.

¹⁹The treatment discontinuation visit should occur 30 days (+7 days) after the last dose of cabozantinib or pembrolizumab (whichever is latest). Most recent scans are used for the treatment discontinuation visit. Note: if a participant initiates a new anti-cancer therapy within 30 days after the last dose of trial

treatment, the treatment discontinuation visit must occur before the first dose of the new therapy and AEs occurring until that point will be collected.

²⁰All patients who were treated will be followed for survival every 4 months with phone calls for up to 3 years from study start date. Patients who came off study for toxicity will be followed for progression with visits or by request of outside medical records every 4 months up to 3 years from study start date, where progression will be assessed by requesting and obtaining subsequent restaging scans. Subsequent anti-neoplastic therapy will be collected if available.

Abbreviations: C, cycle; q2C, every 2 cycles.

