--	--

	
23. Has a known history of HIV infection. Note: HIV testing is not mandated for screening.
 
24. Co-infection with HBV (HBsAg (+) and /or detectable HBV DNA) and HCV (anti-HCV Ab (+) and detectable HCV RNA) at study entry.
 
25. Co-infection with HBV and HDV at study entry.
 
26. Live vaccine or live attenuated vaccine within 30 days prior to first dose of study treatment. Administration of killed vaccines is allowed.
 
27. Pregnant or lactating females.
 
28. Known psychiatric illness, substance abuse disorder, or other condition that would interfere with the ability to comply with the requirements of the study.
 
29. Has history or current evidence of any condition, therapy, or laboratory abnormality that might confound the results of the study, interfere with the subject's participation for the full duration of the study, or is not in the best interest of the subject to participate, in the opinion of the treating investigator.

Study treatments	
All enrolled patients will receive cabozantinib 40mg PO daily continuously and pembrolizumab 200mg IV every 3 weeks, in 3-week cycles. Dose modifications of cabozantinib and/or pembrolizumab may be made for adverse events (AEs) (guidelines provided in protocol). Immune-related AEs will be treated per published guidelines. If one agent needs to be discontinued due to treatment-related toxicity, patients may continue to receive treatment with the other agent.
 
Treatment will continue until disease progression, intolerance, or patient withdrawal. Treatment beyond progression will be allowed if pre-specified criteria are met (Section 12.1).

Study assessments	
Toxicity assessments (history, physical exam, labs) will occur weekly during cycle 1, then every 3 weeks on day 1 of each subsequent cycle. AEs will be graded by NCI CTCAE v5.
 
Disease assessments will be performed by multiphasic contrast CT or MRI of abdomen/pelvis, as well as CT chest with or without contrast at baseline (within one month of enrollment) and every 9 weeks on treatment. Tumor response will be determined by RECIST v1.1 and iRECIST. The tumor marker alpha-fetoprotein (AFP) will also be measured at baseline and every 9 weeks if abnormal at baseline.
 
If patients discontinue treatment due to intolerable or unacceptable toxicity, they will be followed for progression and for survival at least every 4 months up to 3 years.

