11.5 Post-study follow-up

Subjects will return approximately 30 days after their last dose of cabozantinib or pembrolizumab (i.e. treatment discontinuation visit) to complete end-of-study assessments (see Section 11.4). Unused study drug will be returned by the subject. If a participant initiates a new anti-cancer therapy within 30 days after the last dose of trial treatment, the treatment discontinuation visit must occur before the first dose of the new therapy.

All treatment-related AEs will be followed until resolution, return to baseline, or deemed clinically insignificant by the treating investigator, including those that occur during the 30-day period after treatment discontinuation. Moreover, any known SAE attributed to study treatment that occurs more than 30 days after treatment discontinuation must be followed until either resolution, return to baseline, or determination by the investigator that the event has become stable or irreversible; all concomitant medications for these SAEs after 30 days from treatment discontinuation must also be recorded.

For patients who discontinue study treatment due to toxicities or reasons other than progressive disease, subsequent imaging, if available, will be requested every 4 months up to 2 years from study start date to document time of progression after coming off study. For patients who come off study due to progressive disease, patients will be followed for survival every 4 months up to 2 years from study start date (no scans will be required). Moreover, subsequent anti-neoplastic therapy receive after study discontinuation will be collected, if available.

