- Discontinuation of pembrolizumab may be considered for participants who have attained a confirmed CR and have been treated for at least 8 cycles (at least 24 weeks), receiving at least 2 further cycles of cabozantinib and pembrolizumab beyond the date when the initial CR was declared.
- Completion of 2 years of therapy.
- Participant has any of the following non-overdose HECIs that are not reversible and manageable by therapy (see below). (Note: Temporary hepatic decompensation may occur in patients with cirrhosis exposed to TKIs.)
 - ALT >20 × ULN (confirmed within 1 week)
 - Drug-related total bilirubin >10 × ULN
 - CP score of > 8 points
 - Hepatic encephalopathy
 - Recurrence of a severe or life-threatening event, or of any of the laboratory abnormalities listed above, that are presumed to be immune-related
 - Uncontrolled ascites
- Subject is lost to follow-up.

Patients who come off study should be evaluated at 30 days (+ 7 days) after the last dose of cabozantinib or pembrolizumab (whichever is latest). AE assessment and reporting for patients who discontinue study treatment are described in Section 16.3.2. Furthermore, subjects who come off study for reasons other than PD will be followed for progression, and all patients who come off study will be followed for survival every 4 months for up to 2 years from study start date.

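### The protocol names two different groups for progression follow-up after stopping treatment: toxicity exits in the synopsis and study calendar, all non-PD exits in Sections 11.5 and 12.0

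*Combined protocol and SAP*

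**What the plan says.** Three places tie progression follow-up after stopping to toxicity.

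- Synopsis, Study assessments: "If patients discontinue treatment due to intolerable or unacceptable toxicity, they will be followed for progression and for survival at least every 4 months".
- Table 10.1, footnote 14: "For patients who come off study for toxicity, subsequent restaging scans will be requested and assessed at least every 4 months".
- Table 10.1, footnote 20: "Patients who came off study for toxicity will be followed for progression with visits or by request of outside medical records". The sentence before it gives survival calls to every treated patient.

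Two places use a wider group.

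- Section 11.5: "For patients who discontinue study treatment due to toxicities or reasons other than progressive disease, subsequent imaging, if available, will be requested every 4 months".
- Section 12.0: "subjects who come off study for reasons other than PD will be followed for progression".

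The Table 10.1 row "Vital status, date of progression if applicable" is marked at follow-up with no limit by reason for stopping, but footnote 20 governs that column.

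PFS is a secondary endpoint (Section 4.2). It runs from registration to centrally read radiographic progression, clinical progression or death. Section 17.2 estimates it by Kaplan-Meier and states no censoring rule for patients who stop without PD.

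**The concern.** Whether a patient who stops for neither PD nor toxicity has later scans requested depends on which part of the protocol the staff use. Under the calendar such a patient gets survival calls only; under Sections 11.5 and 12.0 scans are requested.

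Without progression follow-up, the analyst has two ways to handle that patient's PFS. One is to censor at stopping, which biases the estimate if leaving is related to prognosis. The other, available because survival is tracked, is to count an event only at death, which is too late whenever progression came first. The plan does not choose between them, and progression dates that were never requested may be hard to recover at analysis.

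**Working it through.** **1. The passages side by side**

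| Place | Followed for progression | Limit |
|---|---|---|
| Synopsis | Stopped for toxicity | 3 years |
| Footnote 14 | Stopped for toxicity | 2 years |
| Footnote 20 | Stopped for toxicity | 3 years |
| Section 11.5 | Toxicity or any other non-PD reason | 2 years |
| Section 12.0 | Any non-PD reason | 2 years (could be read as survival only) |

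The limits conflict as well. That is a separate matter from who is followed.

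**2. Who falls between the two groups.** Section 12.0 lists patient request, significant noncompliance (also Section 7.4), another malignancy, and need for a prohibited treatment. None of these is PD or toxicity.

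**3. The plan's own figures.** The only design calculation is the two-stage response test in Section 17.1. Summing the binomial probability of each stage-1 count x ≥ 3 out of 13, times the probability of at least 9 − x responses among the next 16, gives type I error 0.0999 at a 20% response rate and power 0.804 at 38%. This agrees with the stated 0.10 and 80%. It does not involve follow-up after stopping, so it does not change.

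**4. Size of the PFS error.** The documents give no exit rate and no post-exit hazard, so these are assumptions:

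- a fraction f = 10% or 20% leaves before PD for these reasons (0.10 × 29 = 2.9 and 0.20 × 29 = 5.8, so roughly 3–6 patients);
- median PFS 9.69 months, the lenvatinib/pembrolizumab figure in Section 1.2.5;
- exponential times, with the progression hazard after leaving k times that before;
- death a median 8 months after progression.

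The progression hazard is λ = ln 2 / 9.69 = 0.0715 per month. The exit hazard solves f = δ/(δ + λ), so δ = λf/(1 − f), which is 0.0079 (10%) or 0.0179 (20%).

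With exact follow-up, and with a = λ + δ and b = kλ,

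S(t) = e^(−at) + [δ/(b − a)] × [e^(−at) − e^(−bt)].

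Setting S(t) = 0.5 gives the median with follow-up. Censoring at stopping makes Kaplan-Meier estimate e^(−λt), whose median is 9.69 in every case.

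| k | Median with follow-up, 10% / 20% leaving | Error if censored, 10% / 20% |
|---|---|---|
| 0.5 | 9.90 / 10.18 | −0.2 / −0.5 |
| 1 | 9.69 / 9.69 | 0 / 0 |
| 2 | 9.41 / 9.11 | +0.3 / +0.6 |
| 4 | 9.13 / 8.55 | +0.6 / +1.1 |

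Counting leavers as events only at death was simulated under the same assumptions. For k from 1 to 4 the median is 9.9–10.1 months (10% leaving) or 10.1–10.6 (20%). The excess over exact follow-up runs from 0.4 months (10%, k = 1) to 1.5 months (20%, k = 4).

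**5. Against the follow-up the plan would deliver.** Section 11.5 offers available imaging every 4 months, not exact dates. If post-exit progression is picked up at the next 4-month point, the k = 1 to 4 errors become about −0.3 to +0.6 months (censored) and +0.2 to +0.9 months (event at death).

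**The case against.** **The restriction is implied.** None of the three narrower passages contains the word only, and the wider group includes the toxicity group, so staff who follow Sections 11.5 and 12.0 satisfy every passage. A reader might infer that the calendar forbids progression follow-up of other patients; it does not say so. But footnote 20 sets all treated patients (survival) against toxicity exits (progression). Read on its own, that gives the others survival calls only, and the unrestricted table row does not undo it.

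**Not every non-PD exit is a good example.** Loss of clinical benefit shares a bullet with PD in Section 12.0 and may already be a PFS event as clinical progression under Section 4.2. For symptomatic deterioration, Section 13.1.3 separately asks for objective progression to be documented after stopping. Patients completing 2 years leave far beyond a median near 9.69 months. If the study start date is the patient's own, a 2-year limit leaves them 24 − 24 = 0 months and a 3-year limit 36 − 24 = 12. Neither group is a material example.

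**The direction is not fixed.** It is tempting to say that PFS would be overstated. That holds for counting at death. For censoring it holds only if leavers do worse; at half the hazard, censoring understates the median by 0.2–0.5 months.

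**The effect is modest and local.** With 29 patients, the 95% sampling range of an exponential median of 9.69 months is about 5.5 to 15.7 months. There is one study center, and Section 18.2 requires at least monthly review meetings, so divergence between sites is not the worry. These points limit the consequence; they do not reconcile the passages.

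**Conclusion.** The plan is wrong as written on this point: it contradicts itself on who is followed for progression after stopping. The patients affected are mainly those who leave at their own request, for noncompliance, for a second malignancy or for a prohibited treatment.

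The effect is on the secondary endpoint PFS. Under the stated assumptions it is about a month or less against the follow-up the plan would deliver, and at most 1.5 months against exact follow-up. These sizes rest on an assumed exit rate, post-exit hazard and time to death. The sign of the censoring error cannot be settled from the documents.

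A reader might also infer damage to the primary result, because a response first seen after stopping could be missed. Nothing in the documents allows that to be sized, and the response test is essentially unaffected. The point should be corrected because the error is avoidable and cheap to remove, not because it threatens the trial's main conclusion.

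**What to change.** In the synopsis and in footnotes 14 and 20 of Table 10.1, replace the toxicity wording with *for any reason other than progressive disease*, to match Sections 11.5 and 12.0. Request available restaging scans for all such patients who have not withdrawn consent to follow-up, and have them read centrally. In the same amendment, reconcile the 2-year and 3-year limits and add to Section 17.2 a PFS censoring rule for patients who stop without PD.

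The cost is amended wording plus record requests and central reads for roughly 3–6 more patients at the assumed exit rates. The request mechanism already exists for toxicity exits, and no new procedure is needed.
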